## **HUMAN SUBJECTS RESEARCH**

### **Risk/Benefit Assessment**

#### **Physical risks.**

The risk to human subjects for participation in this study is minimal compared to the potential health benefits they will receive from participating in the moderate-intensity exercise program and receiving detailed health and physical performance evaluations. We do not anticipate any significant physical risks to be associated with participation in this study. Exercise participation has not been previously

associated with serious complications in the general literature or in the experience of [name], whom has directed several exercise trials in older adults with comorbid conditions.

We also have precautions in place to minimize risk of health events during moderate-intensity exercise. We have developed a safe and effective exercise prescription that 1) addresses the frequency, intensity, time, and type—volume and progression principles of exercise prescription, incorporating a progressive transitional phase (i.e., 8-12 weeks), during which the duration and intensity of exercise are gradually increased from light to moderate intensity; 2) includes appropriate warm-up and cool-down procedures; 3) promotes education of warning signs/symptoms to participants and supervisory staff (e.g., chest pain, lightheadedness, unusual shortness of breath); and 4) counsels patients to avoid unaccustomed vigorous to near maximal-intensity physical activity. Additional precautions include: 1) adhering to exercise safety guidelines for hypertension, hyper/hypo-glycemia; 2) individualizing the exercise prescription to account for musculoskeletal injuries and limitations; and 3) monitoring for any problems or possible exercise-related symptoms during the exercise sessions. In addition, participants will be instructed to report any symptoms to the exercise leaders. Participants will be referred to their primary provider if any clinical problem is detected. We followed these same guidelines in our pilot exercise for PTSD study and had no significant adverse events.

The physical performance measures are all sub-maximal, self-paced tests that are age- and ability-appropriate for this patient population and are routinely used in clinical research. The physical performance tests include activities such as walking, standing, stepping, and stretching. These activities reflect common activities of daily living and as such, are associated with minimal risk for injury. However, there is a small risk of falls or muscle soreness with physical testing. To minimize risk of injury, these tests will be performed under supervision of trained research staff following standardized protocols.

The risk of doing moderate-intensity exercise is low, and may be associated with risk of injury, falls, fainting, dizziness, or muscle soreness. There is even the risk of sudden death or stroke. To minimize these risks during exercise, participants will be instructed to exercise at a comfortable level and to never push themselves to a point beyond where they feel safe. Participants will also be monitored and instructed to report symptoms such as unusual shortness of breath, dizziness, tightness or pain in the chest or arms, skipping heart beats, numbness, loss of balance, nausea, or blurred vision. In both conditions, there is a potential risk associated with the loss of confidentiality of study data. While it is

not possible to guarantee confidentiality in the group setting, all participants will be asked to sign a confidentiality agreement stating that disclosure of group member identities to anyone outside the group is not permissible.

We have also developed detailed SOPs in the case of serious adverse events during exercise testing or training (see attached). This includes:

- Calling 911 for emergencies (offsite exercise facility)
- Presence of a defibrillator on-site, and all research staff trained in use
- Glucose monitoring device and testing strips on-site, available as needed
- Daily monitoring of rating of perceived exertion (RPE) during exercise and patient reports of intensity

Risk of injury and adverse health events with exercise are further reduced by the presence of trained supervision (clinical exercise physiologist) at all times, with further support provided by the fitness facility staff trained in CPR and First Aid.

Psychological risks. As part of our assessments we will ask participants about their PTSD and depression symptoms, other aspects of their health, and their demographic characteristics (i.e., race, socioeconomic status). The PTSD assessments (CAPS-5, PCL-5) can cause some psychological distress, but any ensuing distress is usually well tolerated. The PHQ-9 depression survey includes a single item about suicidal ideation. In our pilot feasibility study 20% of patients endorsed this item, though none expressed active suicidality upon further probing from the research staff. [name], who has worked with thousands of Veterans with PTSD, will be available “on page” for consultation and to assist patients in the event any acute issues arise during the CAPS-5 or any other study-related assessments.

Participants will also be referred to their primary provider.

We have developed a Standard Operating Procedure (SOP) for assisting patients that endorse suicidal thoughts and connecting them with services and their provider (see attached). The SOP for suicidal ideation includes:

- Further probing about intent, means, and plan.
- Electronic communication in CPRS that includes the patient’s mental health and primary care providers
- Providing a hand-out that shows the resources available including the Veteran Crisis Line phone number, online chat site, and text response system.

- If suicidal ideation appears active or the patient is in distress they are escorted directly to Psychiatric Emergency Services Clinic (PEC), located in the Durham VA HCS emergency room, to receive immediate care.

In addition, if an individual reveals current intent to harm him/herself or someone else, we will escort (or have escorted) the patient to the hospital's emergency room to be seen by staff in the PEC. In the event this information is revealed over the phone, we will transfer this person directly to the Veterans Crisis Line.

### **Selection of Subjects**

The proposed study will randomize up to 188 patients. Because there may be differences in responses to the intervention by gender, we will stratify randomization by gender. Participants will be Veterans 1) aged 65 years or older; 2) live within a 50 mile radius of DVAMC; and 3) meet diagnostic criteria for PTSD (CAPS-5).

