### **Study Design**

- Study type: Interventional (clinical trial)
- Allocation: Randomized (1:1)
- Intervention model: Parallel assignment
- Masking: Outcomes assessor masked
- Primary purpose: Treatment / behavioral intervention
- Study duration per participant: 6 months

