### **Data Analysis and Statistical Considerations**

*General Considerations.* The basic design of the study is a two-arm parallel group, longitudinal intervention with replicate measures at baseline and 6 months. Randomization to the treatment groups will be stratified by gender. Since subjects are randomized to either EX or HA-ATC, and the groups should be equal at baseline, the analysis is straightforward. The primary and secondary analyses will be conducted on an intent-to-treat (ITT) basis; patients will be analyzed in the group to which they were randomized, regardless of intervention adherence. Additional supporting analyses focusing on alternative, more restrictive analytic cohorts (e.g., per protocol analysis) may be considered for exploratory analyses to provide additional information about the impact of exposure to the intervention. The main conclusions drawn from this trial will be based on the pre-specified primary and secondary hypotheses outlined below and will be tested with two-sided p-values at the standard 0.05 level. Results from exploratory analyses will be interpreted with appropriate consideration for their exploratory nature.

**Primary Analysis (Aim 1).** Our primary hypothesis ( $H_1$ ) is as follows: A 6-month structured exercise program will result in significantly greater improvements in PTSD symptoms (CAPS-5) and physical function (6MWT) when compared to HA-ATC.

**Secondary Analyses (Aim 2).** The secondary hypotheses of this study are:

The 6-month structured exercise program will result in significantly greater improvements in depression (PHQ-9) and sleep quality.

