## **Subject Recruitment**

For the purposes of screening, recruiting, and determining eligibility, information will be obtained through both identifiable private information obtained by accessing VA medical records, and written communication with the prospective participant.

Recruitment and enrollment procedures:

1. *Identify potential participants using EHR.* Potentially eligible participants will be identified through a CDW data pull. Patients meeting age and select clinical eligibility criteria will be mailed an introductory letter.
2. *Health care provider referrals.* We will collaborate with individual providers and program directors across the VISN6 MIRECC and Durham VAHCS specialty care clinics (PTSD, Mental Health, Women's Health, CBOCs) and programs (MOVE!) to recruit patients for this intervention.
3. *Face-to-face recruitment at Veteran organizations and therapy groups.* We have had some success with face-to-face presentations to Veteran support groups in the past, identifying a number of eligible and dedicated participants. We will use this same approach, but will make this a more frequent and deliberate part of our recruitment strategy than previously employed.

Regardless of the recruitment source, all potential participants will receive a telephone call from a research assistant (RA) who will administer a screening questionnaire to assess additional eligibility criteria. Individuals meeting these criteria will be scheduled for a supervised baseline appointment to complete informed consent, HIPAA authorization, and baseline assessments.

***Inclusion of women and minorities.*** We will actively recruit women and minorities to participate in this study (using recruitment methods described above). Based on our previous studies, the demographic characteristics of the Durham VA HCS patient population 65 years and older, and PTSD prevalence estimates in this age cohort, we expect that 8% of the enrolled will be female and 77% African American.

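### Gender stratifies the randomisation but has no stated role in the analysis; naming it as a covariate is a small, nearly free improvement

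*Combined protocol and SAP*

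**What the plan says.** Two sections state the stratification. Selection of Subjects gives the reason: "Because there may be differences in responses to the intervention by gender, we will stratify randomization by gender". The General Considerations paragraph of Data Analysis and Statistical Considerations states the fact: "Randomization to the treatment groups will be stratified by gender".

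Gender does not appear again in the statistical section. No covariate, interaction, subgroup or hypothesis involves it. No analysis model is named for any outcome. The nearest thing to a description is the remark that, because of randomisation, "the groups should be equal at baseline, the analysis is straightforward". Conclusions are tied to the listed aims: "The main conclusions drawn from this trial will be based on the pre-specified primary and secondary hypotheses outlined below", which are to be "tested with two-sided p-values at the standard 0.05 level". Neither the primary nor the secondary hypothesis concerns gender.

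On numbers, Selection of Subjects says "The proposed study will randomize up to 188 patients", and the paragraph on women and minorities under Subject Recruitment says "we expect that 8% of the enrolled will be female and 77% African American".

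**The concern.** Stratifying the randomisation forces the arms to be alike on gender. A standard error from an analysis without gender still allows for a chance imbalance that the design has removed. If gender is related to the outcome, that standard error is too large, confidence intervals are too wide and the test is slightly conservative. The usual remedy is to carry the stratification factor into the model, and the plan does not say that it will.

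What is at stake is a little precision, together with agreement between the design and the analysis. Bias and type I error inflation are not at issue. There is also a secondary matter of wording. The reason given for stratifying refers to differences in response, and stratified randomisation does not by itself test or estimate such a difference.

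**Working it through.** **Inputs from the documents.** At most 188 randomised (Selection of Subjects); 8% women (Subject Recruitment); 1:1 allocation (Study Design); two-sided 0.05 (Data Analysis and Statistical Considerations).

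**Assumptions.** The documents give no power, effect size, SD or dropout, so the figure of 188 cannot be reproduced. I use 80% power (multiplier 1.96 + 0.84 = 2.80), effects in units of the outcome SD, a gender gap *d* of 0.5 to 1.0 SD for illustration, and dropout of 0 to 30%.

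**1. Expected number of women.** 0.08 × 188 = 15.04, so about 15 women (7 or 8 per arm) and 173 men. This is a ceiling, because 188 is a maximum and dropout is not deducted. If 188 are randomised, the binomial 95% range is 8 to 23 women.

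**2. Cost of leaving gender out.** Share of outcome variance due to gender ≈ 0.08 × 0.92 × *d*². The standard error is overstated by the factor 1/√(1 − share).

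| Assumed gap *d* | Variance share | Standard error overstated by |
|---|---|---|
| 0.5 SD | 0.0736 × 0.25 = 1.8% | 1/√(1 − 0.018) = 1.009, or 0.9% |
| 1.0 SD | 0.0736 × 1.00 = 7.4% | 1/√(1 − 0.074) = 1.039, or 3.9% |

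Here *d* is the gap in whatever quantity is analysed. Primary Outcome Measures describes the 6-minute walk outcome as a change in distance. A stable difference between men and women in walking distance cancels in a change score, and a baseline covariate would absorb much of it. Only a gender difference in change would remain, and the documents give no figure for that. The table is therefore an upper illustration for the walk test. The documents give no gender gap for CAPS-5, PHQ-9 or PSQI either.

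**3. What the trial could say about response by gender.** The plan promises no such analysis. These figures bear only on the optional wording.

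- Overall effect detectable: 2.80 × √(4/188) = 0.41 SD.
- Gender-by-arm difference detectable: 2.80 × √(4/15 + 4/173) = 2.80 × 0.538 = 1.51 SD.
- Power for an interaction of 0.5 SD is 15%, and for 1.0 SD it is 46%.
- Effect in women alone, 95% CI half-width with 13 degrees of freedom: 2.16 × √(2/7.52) = 1.11 SD (1.01 SD with the normal multiplier).
- Evaluable participants needed for an interaction of 0.5 SD at 8% women: 2.80² × 4 × (1/0.08 + 1/0.92)/0.25, about 1,710.
- With 10% to 30% dropout (14 down to 11 women), the detectable interaction rises to 1.56 to 1.77 SD.

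**The case against.** The strongest reply is that the plan names no model at all, so it cannot be said to leave gender out. The omission is one consequence of a wider gap, and the eventual model might well include gender. This stands in part. The text does not commit to an unadjusted analysis; its argument from equal groups at baseline only points that way. But a stratification factor should be named when the model is written, and nothing at present requires it.

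A second reply is that the loss is trivial and conservative. That also stands. A standard error at most a few percent too large neither biases the estimate nor inflates type I error. The case for the change is that it costs almost nothing.

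A reader might go further and infer from the stated reason that the trial undertakes to say whether men and women respond differently, and cannot. The documents do not support that. The sentence explains why randomisation is stratified, and stratification delivers the balance. No aim, hypothesis or subgroup analysis promises an answer by gender. The main conclusions are confined to hypotheses that do not mention gender, and the same section says exploratory results will be read as exploratory. The small number of women limits what could be learned about gender, but it breaks no commitment.

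**Conclusion.** The point holds as a minor one. Gender is built into the randomisation and given no role in the analysis, and the reasoning offered suggests an unadjusted comparison. The primary comparison is not biased. The standard error would be overstated by about 0.9% to 3.9% if men and women differ by 0.5 to 1.0 SD in the analysed quantity, and by less in a change-score or baseline-adjusted analysis. That gap is my assumption; the documents contain no figure for it.

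It would be wrong to conclude that the trial's main result is endangered, or that a gender-specific question has been posed and left unanswered. What can be said is narrower: at about 15 women the trial cannot test or usefully estimate a difference in response by gender. That conclusion holds across the dropout range shown.

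**What to change.** In Data Analysis and Statistical Considerations, add: *Gender, the stratification factor, is included as a covariate in every primary and secondary model.* This costs one sentence and one degree of freedom per model, and needs no new data because gender is already recorded for randomisation. It fits naturally wherever the analysis model itself is specified.

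Optional, and wording only: in Selection of Subjects, state that stratification is for balance between arms. Add that any gender-by-arm estimate, if one is reported, is descriptive and given with its confidence interval. This changes no result and does not require an interaction analysis to be added.

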### **Exclusion criteria:**

- 1) history of any psychiatric disorder with severe psychotic features in the past 5 years (e.g., bipolar disorder, mania), as indicated by ICD-10 codes F20-F29 (ICD-9 category 298.9).
- 2) prominent suicidal ideation or hospitalization for suicidality in the previous 6 months
- 3) clinically significant: neurological disorder, systemic illness affecting CNS function, or history of seizure disorder in the past 5 years
- 4) uncontrolled diabetes (defined as: (1) Abnormal fasting plasma glucose  $\geq 126$  mg/dL, random plasma glucose  $\geq 200$  mg/dL AND (2) no active medications for diabetes management (Metformin, insulin, etc.) AND (3) no clinical notes in the patient's EHR indicating monitoring by PCP or Endo for diabetes management).
- 5) end stage liver disease or currently receiving dialysis
- 6) physical disabilities precluding use of exercise equipment (assistive mobility devices acceptable)
- 7) significant cognitive impairment or diagnosis of Alzheimer's Disease or Dementia
- 8) hospitalization or ER visit in the past 6 months for conditions contraindicated for exercise (cardiac event; physical trauma)

We will not exclude patients with PTSD who are currently receiving therapy or patients who are currently taking antidepressant medication, but will apply the following criteria: patients must have been in treatment for at least 2 months, meet symptomatic criteria for inclusion, and do not have plans to discontinue treatment during the course of the trial.

## **Subject Recruitment**

For the purposes of screening, recruiting, and determining eligibility, information will be obtained through both identifiable private information obtained by accessing VA medical records, and written communication with the prospective participant.

Recruitment and enrollment procedures:

1. *Identify potential participants using EHR.* Potentially eligible participants will be identified through a CDW data pull. Patients meeting age and select clinical eligibility criteria will be mailed an introductory letter.
2. *Health care provider referrals.* We will collaborate with individual providers and program directors across the VISN6 MIRECC and Durham VAHCS specialty care clinics (PTSD, Mental Health, Women's Health, CBOCs) and programs (MOVE!) to recruit patients for this intervention.
3. *Face-to-face recruitment at Veteran organizations and therapy groups.* We have had some success with face-to-face presentations to Veteran support groups in the past, identifying a number of eligible and dedicated participants. We will use this same approach, but will make this a more frequent and deliberate part of our recruitment strategy than previously employed.

Regardless of the recruitment source, all potential participants will receive a telephone call from a research assistant (RA) who will administer a screening questionnaire to assess additional eligibility criteria. Individuals meeting these criteria will be scheduled for a supervised baseline appointment to complete informed consent, HIPAA authorization, and baseline assessments.

***Inclusion of women and minorities.*** We will actively recruit women and minorities to participate in this study (using recruitment methods described above). Based on our previous studies, the demographic characteristics of the Durham VA HCS patient population 65 years and older, and PTSD prevalence estimates in this age cohort, we expect that 8% of the enrolled will be female and 77% African American.
